## 11 PHARMACOKINETIC ASSESSMENTS

Pharmacokinetic assessments will be performed [REDACTED]. An alternative blood sampling schedule for infants weighing less than 10 kg, for whom less blood volume should be collected, must be used [REDACTED].

Blood samples will be collected for assessment of PK parameters ( $C_{max}$ ,  $t_{max}$ , AUC, and  $t_{1/2}$ ) if the patient's clinical condition allows. [REDACTED]. Dosing date, time, amount, and infusion time of the 3 previous doses (except for Day 1) prior to a PK sample collection will be recorded in the CRF/eCRF.

**Table 8: Pharmacokinetic Sampling Schedule**

	Study Visit
Blood Sample Collection Time point	[REDACTED]
Preinfusion 	[REDACTED]
EOI 	[REDACTED]
0.5 hour after the EOI 	[REDACTED]
1 hour after the EOI 	[REDACTED]
2 hours after the EOI 	[REDACTED]
3 hours after the EOI 	[REDACTED]
4 hours after the EOI 	[REDACTED]
5 hours after the EOI 	[REDACTED]
24 hours after the EOI 	[REDACTED]

 Two venous blood samples will be collected for the EOI and 4 hours post-EOI time points at any one visit during the Extension Period.

 Venous blood samples collected within 60 minutes prior to start of infusion.

 Venous blood sample must be collected within a window of  $\pm 5$  minutes. (Note the sampling at the EOI time point should not occur prior to the completion of the infusion.)

 Capillary blood samples [REDACTED] collected at EOI and post-EOI prior to the corresponding venous blood sample collection. [REDACTED]

 An optional venous blood sample may be collected 24 hours after the EOI.  
Abbreviation: EOI = end of infusion.

Following recommendation by the SRC for an unscheduled dose adjustment during the 6-Month Initial Treatment Period, or after dose escalation is complete and the patient is returned to a prior dose, blood samples will be collected for assessment of PK parameters as follows [REDACTED]:

- On the first Day the adjusted dose is administered, the patient will be administered study drug in-clinic, and a blood sample will be collected at the EOI ( $\pm 5$  minutes) and at 3 to 4 hours after the EOI. The time of the PK sample collection, the dose administered and the start and stop time of IV infusion are to be recorded in the CRF/eCRF.
- If the visit coincides with a previously scheduled PK sample collection, the previously scheduled PK sample collection for that Day will be cancelled with the exception of capillary blood samples on Day 60. Capillary blood samples on Day 60 will be collected 5 min prior to venous blood samples.

Under no circumstance will the total blood volume obtained exceed the amount considered acceptable for the patient's clinical condition and the institution's guidelines [REDACTED]. If an Investigator decides to deviate from these limits, the deviation must be fully documented and the Investigator should provide justification for the deviation. [REDACTED]

[REDACTED]

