-  WPPSI to be completed only for patients 3 years of age or older. For patients with severe developmental delay, the WPPSI may not be an appropriate assessment, and therefore, the Bayley-III may be administered instead.
-  At the first study visit in the Screening Period, the frequency of seizures over the prior month will be collected by recall and a seizure diary will be dispensed. The parent/legal guardian is to enter seizure data (incidence) in the seizure diary each Day for the entire duration of the study. Collect seizure diary at all visits, record seizure data in the CRF/eCRF, and dispense a new diary to the parent/legal guardian.
-  May provide a previous MRI assessment if performed within 6 months prior to enrollment and the patient has remained stable. Neuroimaging will be conducted [REDACTED] if clinical condition allows (additional scans may be requested as needed). Magnetic resonance imaging is the preferred imaging modality, but a computed tomography scan is acceptable if a patient's clinical status does not allow for an MRI. Copies of the scan data will be collected. [REDACTED]
-  May provide previous assessment if performed within 6 months prior to enrollment and the patient's seizure frequency has not changed significantly since that study. Perform standard EEG [REDACTED]. Additional EEGs may be performed at the discretion of the treating physician.
-  Collect a urine sample [REDACTED] for evaluation of SSC, [REDACTED]
-  If an unscheduled dose adjustment is recommended by the SRC, or after dose escalation is complete and the patient is returned to a prior dose based on the patient's clinical status at the discretion of the treating physician after consultation with the SRC, see [Table 5](#) for additional assessments.
-  Two samples must be collected [REDACTED] 2 separate visits (i.e., 1 collection at each visit) during the Screening Period.
-  Sample to be collected prior to first infusion. If a baseline sample was collected on Day -1, the Day 1 sample should be collected only after at least 24 hours have elapsed.
-  Collect a venous blood sample [REDACTED] for PD analysis. If collected on the same Day as neurocognitive assessments, collect blood after assessments.
-  Collect venous blood samples [REDACTED] preinfusion, EOI, and 4 hours post-EOI ( $\pm 5$  minutes for all time points).

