-  Collect venous blood samples [REDACTED] at EOI, 0.5, 1, 2, 3, and 5 hours post-EOI ( $\pm 5$  minutes for all time points).
-  Daily IV infusions of ORGN001 (24 hours  $\pm$  3 hours apart) occur either while in-patient or at home.
-  Changes in seizure medications, including the reason for the change, will be recorded.
-  Additional BP measurements are to be conducted prior to the infusion and at 30, 60, 90, and 120 minutes post-EOI, followed by hourly assessments until 6 hours post-EOI, then every 6 hours until the next dose.
-  Additional BP measurements are to be conducted prior to the infusion and hourly post EOI for 6 hours, then every 6 hours until the next dose. The SRC will review the blood pressure data along with all the other safety data to determine if continued frequent monitoring is needed.
-  An optional blood sample and urine sample will be collected at 24 hours after the EOI for PK and PD assessments.
- Abbreviations: AEs = adverse events; Bayley-III = Bayley Scales of Infant and Toddler Development-Third Edition; BP = blood pressure; CRF = case report form; EEG = electroencephalogram; eCRF = electronic case report form; EOI = end of infusion; GMFCS = Gross Motor Function Classification System; meds =

medications; MoCD = molybdenum cofactor deficiency; MRI = magnetic resonance imaging; PD = pharmacodynamics; PI = principal investigator; PK = pharmacokinetics; rcPMP = recombinant *E. coli*-derived cPMP; SRC = Safety Review Committee; SSC = S-sulfocysteine; WPPSI = Wechsler Preschool and Primary Scale of Intelligence.

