 Collect a venous blood sample [REDACTED] for PD analysis. If collected on the same Day as neurocognitive assessments, collect blood after assessments. [REDACTED]

 Collect capillary blood samples [REDACTED] at the EOI and 4 hours post-EOI prior to collection of the corresponding venous blood samples. Collect venous blood samples [REDACTED] within 5 minutes of the corresponding capillary blood samples, if possible, at the EOI and 4 hours post-EOI.

 Collect venous blood samples [REDACTED] at the EOI ( $\pm 5$  minutes) and 4 hours post-EOI ( $\pm 5$  minutes).

 Daily IV infusion of ORGN001 (24 hours  $\pm$  3 hours apart) occurs at home.

 Daily IV infusion of ORGN001 (24 hours  $\pm$  3 hours apart) occurs while in-clinic.

 Daily IV infusion of ORGN001 (24 hours  $\pm$  3 hours apart) can occur at home or while in-clinic

 Changes in seizure medications, including the reason for the change, will be recorded.

 Assessed only if the patient is seen in-clinic. An in-clinic visit is not required for blood and urine collection on this day.

Abbreviations: AEs = adverse events; Bayley-III = Bayley Scales of Infant and Toddler Development-Third Edition; CRF = case report form; EEG = electroencephalogram; eCRF = electronic case report form; EOI = end of infusion; GMFCS = Gross Motor Function Classification System; meds = medications; MRI = magnetic resonance imaging; PD = pharmacodynamics; PK = pharmacokinetics; rcPMP = recombinant E. coli-derived cPMP; SRC = Safety Review Committee; SSC = S-sulfocysteine; WPPSI = Wechsler Preschool and Primary Scale of Intelligence.

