### 6.5 Study Drug Administration

Starting on Day 1, patients will begin daily IV infusions of ORGN001 at the same dose as their current dose of rcPMP, approximately 24 hours ( $\pm 3$  hours) after their last treatment with rcPMP. [REDACTED]

[REDACTED] The parent or legal guardian will be trained on proper storage, preparation, and administration of study drug for dosing at home [REDACTED].

[REDACTED]. All doses will be administered by IV infusion at a rate of 1.5 mL/minute. [REDACTED]

[REDACTED]

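### Only Table 8 bars an end-of-infusion PK sample before the infusion is complete; four other statements allow it up to 5 minutes early, and the Day 60 capillary timing fits the other capillary rules at a single moment only

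*Protocol*

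**What the plan says.** **Venous EOI sample.** Table 8 footnote 3 gives a ±5-minute window and then restricts it at EOI: "Note the sampling at the EOI time point should not occur prior to the completion of the infusion". In effect the EOI window there is 0 to +5 minutes. Four other statements carry no such restriction:

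- Table 3 footnote 29: "preinfusion, EOI, and 4 hours post-EOI ( $\pm 5$ minutes for all time points".
- Table 3 footnote 30: "at EOI, 0.5, 1, 2, 3, and 5 hours post-EOI ( $\pm 5$ minutes for all time points".
- Table 4 footnote 19: "at the EOI ( $\pm 5$ minutes) and 4 hours post-EOI ( $\pm 5$ minutes".
- Section 11, first bullet under Table 8, on unscheduled dose adjustments: EOI ±5 minutes, plus a sample 3 to 4 hours later.

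**Capillary sample.** Table 4 footnote 18 puts the capillary sample at EOI, before the venous one, with the venous draw within 5 minutes of it if possible. Table 8 footnote 4 also puts it at EOI, ahead of the venous sample. The second bullet under Table 8, on a dose-adjustment visit that coincides with scheduled PK, says: "Capillary blood samples on Day 60 will be collected 5 min prior to venous blood samples".

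**Infusion and use of the result.** Section 6.5 fixes the rate: "All doses will be administered by IV infusion at a rate of 1.5 mL/minute". The infused volume is not visible. Under Section 3.3, exposure above the NOAEL AUC ends escalation. Under Section 3.4.1, Scenario 4, it leads to a dose reduction.

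**The concern.** Concentration rises until the infusion ends, so a sample taken before that point can only read low. A site working from the schedule in Table 3 or Table 4, or from the dose-adjustment bullet, could draw 5 minutes early and be fully compliant, yet breach Table 8. The EOI value is the expected Cmax and also feeds AUC. Its weight in AUC is greatest where only two samples are taken. Such visits exist: Table 4 footnotes 18 and 19, the dose-adjustment bullet and the Extension Period sampling (Appendix C, Table 11, footnote 2) all name EOI and a sample at about 4 hours. Because AUC is compared with the NOAEL limit, the error runs towards understating exposure.

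The capillary issue is separate. If the EOI capillary sample is drawn during the infusion and the venous one after it, the two differ through timing alone.

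**Working it through.** The documents state no PK figure to reproduce, so this checks how far an early draw moves the result.

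**Inputs**
- Rate 1.5 mL/min (Section 6.5). Five minutes is 5 × 1.5 = 7.5 mL not yet given.
- Infusion duration T: assumed, because the volume is not visible. Range 2 to 60 minutes (3 to 90 mL).
- Half-life: under 1 h in adult rats and dogs (Section 1.2). No patient value is given. Assumed 0.5, 1 and 2 h.
- Full schedule: EOI, 0.5, 1, 2, 3 and 5 h (Table 3 footnote 30). Two-sample schedule: EOI and 4 h.

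**Model.** One compartment, constant-rate infusion, k = ln 2 / half-life. For T above 5 minutes:

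C(−5 min) / C(EOI) = [1 − exp(−k(T − 5))] / [1 − exp(−kT)]

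For T of 5 minutes or less the sample is at or before the start of infusion and reads zero.

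**Worked case: T = 10 min, half-life 1 h.** k = 0.6931/60 = 0.01155 per minute. The ratio is (1 − exp(−0.0578)) / (1 − exp(−0.1155)) = 0.0561/0.1091 = 0.514.

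For the two-sample AUC (linear trapezoid, nominal times), set C(EOI) = 1, so C(4 h) = exp(−0.01155 × 240) = 0.0625.
- Exact EOI sample: 10/2 × 1 + 240/2 × (1 + 0.0625) = 5 + 127.5 = 132.5.
- Early sample: 5 × 0.514 + 120 × (0.514 + 0.0625) = 2.57 + 69.18 = 71.75.
- Ratio: 71.75/132.5 = 0.54.

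**Results.** Each entry is the value from a draw 5 minutes early as a percentage of the value from an exact EOI draw. Ranges run over the three half-lives and over linear and linear-log trapezoids. The full schedule covers actual and nominal times; the two-sample AUC uses nominal times only.

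| Infusion | EOI concentration | AUC, EOI and 4 h only | AUC(0-5 h), full schedule |
|---|---|---|---|
| up to 5 min (up to 7.5 mL) | 0 | 0-23 | 64-90 |
| 10 min (15 mL) | 51-53 | 53-67 | 82-95 |
| 20 min (30 mL) | 76-79 | 78-84 | 91-98 |
| 30 min (45 mL) | 85-88 | 86-90 | 94-98 |
| 60 min (90 mL) | 93-96 | 94-96 | 98-99 |

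**With the Table 8 restriction applied everywhere**, the worst case is a draw at +5 minutes. EOI concentration is then 89%, 94% or 97% of the exact value for half-lives of 0.5, 1 and 2 h, whatever the infusion length. Full-schedule AUC is 92-98% (linear-log, actual times).

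**Capillary timing.** Let the venous EOI draw be v minutes after EOI. The Day 60 sentence puts the capillary draw at v − 5. Table 8 allows v from 0 to +5, so the capillary draw lies between −5 and 0. It meets the rule of capillary at EOI only when v = +5. Under the unrestricted ±5-minute window, v runs from −5 to +5 and the capillary draw from −10 to 0.

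**The case against.** The strongest reply is that Table 8 does not contradict the other statements. It gives the same ±5 minutes and narrows it at EOI, in the section that governs PK. No rule calls for a draw during the infusion, and the dose-adjustment bullet sits directly under Table 8. That is a fair account of the intent. It does not help a site that works from Table 3 or Table 4, where the restriction is absent.

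A reader might infer that AUC is far too low in general and that escalation will pass the NOAEL limit unnoticed. The documents do not support that. The infused volume, the patient half-life and the visit columns of the PK schedule are not visible. Nor is the way AUC is derived at two-sample visits: Protocol Section 13.9 says non-compartmental where possible, and SAP Section 6.4 allows PK/PD modelling. Take an AUC that would be 1.3 times the limit with an exact EOI sample. At a 10-minute infusion it would read 1.3 × 0.53 = 0.69 to 1.3 × 0.67 = 0.87 from two samples, but 1.3 × 0.82 = 1.07 to 1.3 × 0.95 = 1.24 from the full schedule. At 20 minutes, even two samples give 1.3 × 0.78 = 1.01 to 1.3 × 0.84 = 1.09. A smaller excess would be hidden more easily. PK is also not the only control: under Section 3.3 the SRC and DMC review safety laboratory and clinical data, and predicted exposure is a separate stopping condition.

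A reader might also infer that the Day 60 sentence lowers AUC. It concerns capillary samples, at a coinciding dose-adjustment visit, and nothing visible says that capillary values enter AUC or the NOAEL comparison.

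Finally, the dose-adjustment bullet already requires the sample time and the infusion start and stop times to be recorded, so an early draw there can be identified. Identification does not restore the missed peak: in the non-compartmental calculation, actual times recover little of the loss.

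**Conclusion.** The inconsistency is in the text and should be removed. Four statements permit an EOI draw up to 5 minutes before the infusion ends, and one forbids it. The direction of the bias is certain: downward for EOI concentration, Cmax and AUC. Its size is conditional. For infusions of about 10 minutes or less, the early reading is roughly half the EOI concentration or lower, and a large loss of AUC also needs a two-sample visit. At 20 minutes or longer, the full-schedule AUC loss is 9% or less. These figures rest on a one-compartment model, assumed infusion durations, assumed half-lives of 0.5 to 2 h and a draw at the full 5 minutes early, so they show a range and do not predict what happened in this trial.

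The capillary rules can all be met at one moment only, with the capillary draw at EOI and the venous draw at exactly +5 minutes. At any earlier venous draw that follows the Day 60 sentence, the EOI capillary sample precedes EOI and the capillary-venous comparison is confounded by timing. Venous AUC is unaffected.

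**What to change.** 1. Carry the Table 8 restriction (EOI sample at 0 to +5 minutes after completion of the infusion) into Table 3 footnotes 29 and 30, Table 4 footnote 19 and the Section 11 dose-adjustment bullet.
2. Reconcile the Day 60 capillary sentence with Table 4 footnote 18 and Table 8 footnote 4, so that both the capillary and the venous EOI samples follow completion of the infusion, with actual times recorded.
3. In the PK analysis, flag any EOI sample drawn before completion and report the resulting Cmax and AUC as likely underestimates, including where they are supplied to the SRC and DMC. Excluding such samples from the NOAEL comparison is not advised: at an EOI and 4 h visit that would leave one concentration and no AUC.

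The cost is wording in three footnotes, one bullet and one sentence, plus one data-handling rule in the PK analysis plan. It needs no extra samples or blood volume.

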## 12 SAFETY ASSESSMENTS

Safety assessments will be performed [REDACTED]. If multiple assessments of a single parameter are performed within a time period (i.e., multiple measurements of laboratory assessments on Day 1), further instruction will be provided in the CRF/eCRF manual as to which data to collect.

### 12.1 Vital Signs

Vital signs will be taken [REDACTED]. On Day 1, vital signs are to be taken within 24 hours prior to infusion. Vital signs will include heart rate, respiratory rate, BP, and temperature.

#### 12.1.1 Additional Blood Pressure Measurements

All additional BP measurements [REDACTED] must be recorded in the CRF/eCRF [REDACTED].

### 12.2 Physical Examination

A complete physical examination [REDACTED] will be performed [REDACTED]. On Day 1, the physical examination is to be performed within 24 hours prior to infusion.

Ascites and hepatic encephalopathy scores will be recorded [REDACTED] and the Child-Pugh score will be calculated.

Assign a score of 1, 2 or 3 for each of the following categories according to the criteria in Table 9. The total of the scores determines the Child-Pugh score as Grade A (5--6), Grade B (7-9), or Grade C (10-15).

**Table 9: Criteria for Child-Pugh Classification**

Clinical or Biochemical Measurements	Points Scored for Increasing Abnormality			Enter Assigned Score
	1	2	3	
Hepatic encephalopathy (grade)	Absent	1 and 2	3 and 4	
Ascites	Absent	Mild	Moderate	
Total bilirubin (mg/dl)	<2.0	2.0-3.0	>3.0	
Serum albumin (g/dl)	>3.5	2.8-3.5	<2.8	
Prothrombin time INR	<1.7	1.7-2.3	>2.3	
	Total Score			

Abbreviation: INR=International normalized ratio

### 12.3 Laboratory Assessments

Blood samples will be collected for analysis of hematology, serum chemistry and coagulation parameters. Urine samples will be collected for urinalysis. [REDACTED]. The PI or delegate will review, sign and date laboratory reports as well as indicating if abnormal results are clinically significant or not clinically significant.

Abnormal results will be followed up at the discretion of the Investigator. An alternative blood sampling schedule for infants weighing less than 10 kg, for whom less blood volume should be collected, must be used [REDACTED].

Following recommendation by the SRC for an unscheduled dose adjustment during the 6-Month Initial Treatment Period, or after dose escalation is complete and the patient is returned to a prior dose blood and urine samples will be collected for assessment of hematology, serum chemistry, and urinalysis as follows [REDACTED]:

- Seven days after the adjusted dose is administered at the [REDACTED] Follow-up Visit, the study drug will be administered in-clinic. A blood and a urine sample will be collected at any time during this study visit.

[REDACTED]

[REDACTED]

Under no circumstance will the total blood volume obtained exceed the amount considered acceptable for the patient's clinical condition and the institution's guidelines [REDACTED]. If an Investigator decides to deviate from these limits, the deviation must be fully documented and the Investigator should provide justification for the deviation. [REDACTED]

#### 12.3.1 Hematology

Blood samples will be collected [REDACTED]. On Day 1, the blood sample is to be taken within 24 hours prior to infusion. Samples will be analyzed for a complete blood count which includes: platelet count, red blood cell (RBC) count, white blood cell (WBC) count and automated differential (neutrophils, lymphocytes, monocytes, eosinophils, and basophils), hemoglobin, hematocrit, RBC indices (mean corpuscular volume, mean corpuscular hemoglobin, and mean corpuscular hemoglobin concentration).

#### 12.3.2 Serum Chemistry

Blood samples will be collected [REDACTED]. On Day 1, the blood sample is to be taken within 24 hours prior to infusion. Samples will be analyzed for the following serum chemistry parameters: sodium, potassium, bicarbonate, chloride, blood urea nitrogen, creatinine, calcium, alanine aminotransferase, aspartate aminotransferase, alkaline phosphatase, total bilirubin, serum osmolality, and total serum albumin.

### 12.3.3 Coagulation

Blood samples will be collected [REDACTED]. On Day 1, the blood sample may be taken within 24 hours prior to infusion. Samples will be analyzed for PT and the INR.

### 12.3.4 Urinalysis

Urine samples will be collected [REDACTED]. Samples will be analyzed for the following parameters: specific gravity, pH, glucose, protein, blood and ketones (by dipstick and microscopic examination), and urine protein to creatinine ratio.

## 12.4 Electroencephalogram

Standard EEGs [REDACTED] will be performed [REDACTED]. However, additional EEGs may be performed at the discretion of the treating physician, and EEGs [REDACTED] are only to be performed if clinically indicated. Results from a previous EEG may be provided in lieu of performing an EEG during the Screening Period if the previous assessment was performed within 6 months prior to enrollment and the patient's seizure frequency has not changed significantly since that study. If applicable, the previous EEG findings will be collected and will include the overall interpretation of the specific abnormality (as applicable), and date and time of each evaluation.

## 12.5 Adverse Event Management

The Investigator is responsible for detecting, assessing, documenting and reporting of all AEs. All AEs will be recorded from the signing of informed consent, until study completion.

Note: There is no time limit for SAEs that are considered causally related.

All observed or volunteered AEs regardless of causal relationship must be reported and recorded in the CRF/eCRF. Adverse events reported by the patient and/or parent or legal guardian and/or identified in response to an open-ended question from study personnel or revealed by observation, physical examination, or other study procedures must be collected and recorded.

### 12.5.1 Definition of an Adverse Event

An AE is defined as any unfavorable and unintended sign (eg, including an abnormal laboratory finding), symptom or disease temporally associated with the use of a medicinal product or procedure, whether or not considered related to the medicinal product or procedure that occurs during the course of the clinical study.

Exacerbations of a chronic or intermittent pre-existing condition including either an increase in frequency and/or intensity of the condition are all to be considered AEs.

Abnormal test findings may be considered AEs. If an abnormal laboratory value is identified, Investigators are strongly encouraged to report a diagnosis, or a sign or symptom rather than an isolated abnormal test value. An abnormal test finding should be documented as an AE if any of the following conditions are met:

- Is associated with a sign or symptom;
- Requires additional diagnostic testing (repeat tests are not considered additional testing);
- Requires a medical or surgical intervention;

- Leads to a change in study dosing outside of the protocol defined dosing or discontinuation from the study;
- Requires significant additional treatment;
- Does not meet any of the conditions above; however, the Investigator or Sponsor considers the result as clinically significant or meeting the definition of an AE.

This definition also includes the signs or symptoms resulting from:

- Drug overdose
- Drug withdrawal
- Drug misuse
- Drug interactions
- Extravasation
- Medication error
- Occupational exposure

An AE does not necessarily include the following:

- Medical or surgical procedures (eg, surgery, endoscopies, tooth extraction, transfusion); the condition that leads to the procedure is the AE (eg, laparoscopic cholecystectomy is the procedure or treatment for an SAE of necrotic gall bladder);
- Pre-existing diseases or conditions present or detected prior to the Screening evaluation that do not worsen;
- Situations where an untoward medical occurrence has not occurred (eg, hospitalization for elective surgery if planned prior to the start of the study, social and/or convenience admissions).

